## Incyte Corporation INCAGN 1876-101 Statistical Analysis Plan

PROTOCOL: INCAGN 1876-101

DRUG/INDICATION: INCAGN01876/Advanced or Metastatic Solid Tumors

TLF VERSION: Draft

Table 3.3.2.1

Shift Summary of Hematology Laboratory Values in CTC Grade - To the Worst Abnormal Value (Population: Part 1 FAS Population)

Laboratory Test (unit): xxxxxxxx (xxxxx)

|                    | Basel   | line[1]   |           | Wo       | rst Post-Ba | seline Valu | e [2]    |          |
|--------------------|---------|-----------|-----------|----------|-------------|-------------|----------|----------|
| Dose Level (mg/kg) | Grade   | n (%)     | Grade 0   | Grade 1  | Grade 2     | Grade 3     | Grade 4  | Missing  |
| 1.0                | Grade 0 | xxx xx.x% | XXX XX.X% | XX XX.X% | XX XX.X%    | XX XX.X%    | XX XX.X% | XX XX.X% |
|                    | Grade 1 | XXX XX.X% | XXX XX.X% | xx xx.x% | xx xx.x%    | XX XX.X%    | XX XX.X% | xx xx.x% |
|                    | Grade 2 | XXX XX.X% | XXX XX.X% | xx xx.x% | xx xx.x%    | XX XX.X%    | XX XX.X% | xx xx.x% |
|                    | Grade 3 | XXX XX.X% | XXX XX.X% | xx xx.x% | xx xx.x%    | XX XX.X%    | XX XX.X% | xx xx.x% |
|                    | Grade 4 | XXX XX.X% | XXX XX.X% | xx xx.x% | xx xx.x%    | XX XX.X%    | XX XX.X% | xx xx.x% |
|                    | Missing | XXX XX.X% | XXX XX.X% | XX XX.X% | xx xx.x%    | xx xx.x%    | XX XX.X% | xx xx.x% |
|                    | Total   | xxx xx.x% | XXX XX.X% | XX XX.X% | XX XX.X%    | XX XX.X%    | XX XX.X% | XX XX.X% |
| 3.0                | Grade 0 | xxx xx.x% | xxx xx.x% | xx xx.x% | xx xx.x%    | xx xx.x%    | xx xx.x% | xx xx.x% |
|                    | Grade 1 | XXX XX.X% | XXX XX.X% | xx xx.x% | xx xx.x%    | XX XX.X%    | XX XX.X% | xx xx.x% |
|                    | Grade 2 | XXX XX.X% | XXX XX.X% | xx xx.x% | xx xx.x%    | XX XX.X%    | XX XX.X% | xx xx.x% |
|                    | Grade 3 | XXX XX.X% | xxx xx.x% | xx xx.x% | xx xx.x%    | xx xx.x%    | xx xx.x% | xx xx.x% |
|                    | Grade 4 | XXX XX.X% | XXX XX.X% | XX XX.X% | xx xx.x%    | xx xx.x%    | xx xx.x% | xx xx.x% |
|                    | Missing | XXX XX.X% | XXX XX.X% | XX XX.X% | xx xx.x%    | xx xx.x%    | xx xx.x% | xx xx.x% |
|                    | Total   | XXX XX.X% | XXX XX.X% | xx xx.x% | xx xx.x%    | XX XX.X%    | XX XX.X% | xx xx.x% |

FOLDER\PROGRAM\OUTPUT: XXXXXX\XXXXXX.SAS\XXXXXX.LST

[1] The percentages for the baseline column were calculated using the baseline total as the denominator.

[2] For each row, the percentages were calculated using the number of subjects with a given grade at baseline as the denominator.

Worst post-baseline laboratory value was the worst grade observed post-baseline for a given subject.

DATE (TIME): MMDDYYYY (hh:mm)

## Incyte Corporation INCAGN 1876-101 Statistical Analysis Plan

PROTOCOL: INCAGN 1876-101 (Page n of N)
DRUG/INDICATION: INCAGN01876/Advanced or Metastatic Solid Tumors DATABASE VERSION: XXXXXX2016

TLF VERSION: Draft

Table 3.3.2.1

Shift Summary of Hematology Laboratory Values in CTC Grade - To the Worst Abnormal Value (Population: Part 1 FAS Population)

Laboratory Test (unit): xxxxxxxx (xxxxx)

|                    | Basel   | line[1]   |           | Wo       | rst Post-Ba | seline Valu | e [2]    |          |
|--------------------|---------|-----------|-----------|----------|-------------|-------------|----------|----------|
| Dose Level (mg/kg) | Grade   | n (%)     | Grade 0   | Grade 1  | Grade 2     | Grade 3     | Grade 4  | Missing  |
| 5.0                | Grade 0 | XXX XX.X% | XXX XX.X% | XX XX.X% | XX XX.X%    | XX XX.X%    | XX XX.X% | XX XX.X% |
|                    | Grade 1 | XXX XX.X% | XXX XX.X% | xx xx.x% | xx xx.x%    | xx xx.x%    | XX XX.X% | xx xx.x% |
|                    | Grade 2 | XXX XX.X% | XXX XX.X% | xx xx.x% | xx xx.x%    | xx xx.x%    | XX XX.X% | xx xx.x% |
|                    | Grade 3 | XXX XX.X% | XXX XX.X% | xx xx.x% | xx xx.x%    | xx xx.x%    | XX XX.X% | xx xx.x% |
|                    | Grade 4 | XXX XX.X% | XXX XX.X% | xx xx.x% | xx xx.x%    | xx xx.x%    | XX XX.X% | xx xx.x% |
|                    | Missing | XXX XX.X% | XXX XX.X% | xx xx.x% | xx xx.x%    | xx xx.x%    | XX XX.X% | xx xx.x% |
|                    | Total   | xxx xx.x% | XXX XX.X% | XX XX.X% | XX XX.X%    | XX XX.X%    | XX XX.X% | XX XX.X% |
| 10.0               | Grade 0 | xxx xx.x% | xxx xx.x% | xx xx.x% | xx xx.x%    | xx xx.x%    | xx xx.x% | xx xx.x% |
|                    | Grade 1 | XXX XX.X% | XXX XX.X% | xx xx.x% | xx xx.x%    | xx xx.x%    | XX XX.X% | xx xx.x% |
|                    | Grade 2 | XXX XX.X% | XXX XX.X% | xx xx.x% | xx xx.x%    | xx xx.x%    | XX XX.X% | xx xx.x% |
|                    | Grade 3 | XXX XX.X% | xxx xx.x% | xx xx.x% | xx xx.x%    | xx xx.x%    | xx xx.x% | xx xx.x% |
|                    | Grade 4 | XXX XX.X% | XXX XX.X% | xx xx.x% | xx xx.x%    | XX XX.X%    | xx xx.x% | xx xx.x% |
|                    | Missing | XXX XX.X% | XXX XX.X% | xx xx.x% | xx xx.x%    | XX XX.X%    | xx xx.x% | xx xx.x% |
|                    | Total   | XXX XX.X% | XXX XX.X% | xx xx.x% | xx xx.x%    | xx xx.x%    | XX XX.X% | xx xx.x% |

FOLDER\PROGRAM\OUTPUT: XXXXXX\XXXXXX.SAS\XXXXXX.LST

[1] The percentages for the baseline column were calculated using the baseline total as the denominator.

[2] For each row, the percentages were calculated using the number of subjects with a given grade at baseline as the denominator.

Worst post-baseline laboratory value was the worst grade observed post-baseline for a given subject.

PROTOCOL: INCAGN 1876-101 (Page n of N)
DRUG/INDICATION: INCAGN01876/Advanced or Metastatic Solid Tumors DATABASE VERSION: XXXXX2016

TLF VERSION: Draft

Table 3.3.2.1

Shift Summary of Hematology Laboratory Values in CTC Grade - To the Worst Abnormal Value (Population: Part 1 FAS Population)

Laboratory Test (unit): xxxxxxxx (xxxxx)

|                    | Base    | line[1]   | Worst Post-Baseline Value [2] |          |          |          |          |          |  |  |  |  |
|--------------------|---------|-----------|-------------------------------|----------|----------|----------|----------|----------|--|--|--|--|
| Dose Level (mg/kg) | Grade   | n (%)     | Grade 0                       | Grade 1  | Grade 2  | Grade 3  | Grade 4  | Missing  |  |  |  |  |
| 
Total          | Grade 0 | XXX XX.X% | XXX XX.X%                     | XX XX.X% | xx xx.x% | XX XX.X% | XX XX.X% | XX XX.X% |  |  |  |  |
|                    | Grade 1 | XXX XX.X% | xxx xx.x%                     | xx xx.x% | xx xx.x% | XX XX.X% | xx xx.x% | xx xx.x% |  |  |  |  |
|                    | Grade 2 | XXX XX.X% | xxx xx.x%                     | xx xx.x% | xx xx.x% | XX XX.X% | xx xx.x% | xx xx.x% |  |  |  |  |
|                    | Grade 3 | XXX XX.X% | xxx xx.x%                     | xx xx.x% | xx xx.x% | XX XX.X% | xx xx.x% | xx xx.x% |  |  |  |  |
|                    | Grade 4 | XXX XX.X% | xxx xx.x%                     | xx xx.x% | xx xx.x% | xx xx.x% | xx xx.x% | xx xx.x% |  |  |  |  |
|                    | Missing | XXX XX.X% | xxx xx.x%                     | xx xx.x% | xx xx.x% | xx xx.x% | xx xx.x% | xx xx.x% |  |  |  |  |
|                    | Total   | xxx xx.x% | xxx xx.x%                     | xx xx.x% | xx xx.x% | xx xx.x% | xx xx.x% | xx xx.x% |  |  |  |  |

FOLDER\PROGRAM\OUTPUT: XXXXXXXXXXXX.SAS\XXXXXX.LST

DATE(TIME): MMDDYYYY(hh:mm)

[1] The percentages for the baseline column were calculated using the baseline total as the denominator.

[2] For each row, the percentages were calculated using the number of subjects with a given grade at baseline as the denominator.

Worst post-baseline laboratory value was the worst grade observed post-baseline for a given subject.

DATE (TIME): MMDDYYYY (hh:mm)

## Incyte Corporation INCAGN 1876-101 Statistical Analysis Plan

PROTOCOL: INCAGN 1876-101 (Page n of N)
DRUG/INDICATION: INCAGN01876/Advanced or Metastatic Solid Tumors DATABASE VERSION: XXXXX2016

TLF VERSION: Draft

Table 3.3.2.2

Shift Summary of Hematology Laboratory Values in CTC Grade - To the Worst Abnormal Value (Population: Part 2 FAS Population)

Laboratory Test (unit): xxxxxxxx (xxxxx)

|             | Base    | line[1]   |           | Wo       | rst Post-Ba | seline Valu | e [2]    |          |
|-------------|---------|-----------|-----------|----------|-------------|-------------|----------|----------|
| Cancer Type | Grade   | n (%)     | Grade 0   | Grade 1  | Grade 2     | Grade 3     | Grade 4  | Missing  |
| Endometrium | Grade 0 | xxx xx.x% | XXX XX.X% | XX XX.X% | XX XX.X%    | XX XX.X%    | XX XX.X% | XX XX.X% |
|             | Grade 1 | XXX XX.X% | xxx xx.x% | XX XX.X% | xx xx.x%    | XX XX.X%    | xx xx.x% | XX XX.X% |
|             | Grade 2 | XXX XX.X% | xxx xx.x% | XX XX.X% | xx xx.x%    | XX XX.X%    | xx xx.x% | XX XX.X% |
|             | Grade 3 | XXX XX.X% | xxx xx.x% | XX XX.X% | xx xx.x%    | XX XX.X%    | xx xx.x% | XX XX.X% |
|             | Grade 4 | XXX XX.X% | xxx xx.x% | XX XX.X% | xx xx.x%    | XX XX.X%    | xx xx.x% | XX XX.X% |
|             | Missing | xxx xx.x% | xxx xx.x% | xx xx.x% | xx xx.x%    | xx xx.x%    | xx xx.x% | xx xx.x% |
|             | Total   | xxx xx.x% | xxx xx.x% | XX XX.X% | XX XX.X%    | XX XX.X%    | XX XX.X% | XX XX.X% |
| Melanoma    | Grade 0 | xxx xx.x% | xxx xx.x% | xx xx.x% | xx xx.x%    | xx xx.x%    | xx xx.x% | xx xx.x% |
|             | Grade 1 | XXX XX.X% | xxx xx.x% | XX XX.X% | xx xx.x%    | XX XX.X%    | xx xx.x% | XX XX.X% |
|             | Grade 2 | xxx xx.x% | xxx xx.x% | xx xx.x% | xx xx.x%    | xx xx.x%    | xx xx.x% | xx xx.x% |
|             | Grade 3 | xxx xx.x% | xxx xx.x% | xx xx.x% | xx xx.x%    | xx xx.x%    | xx xx.x% | xx xx.x% |
|             | Grade 4 | xxx xx.x% | xxx xx.x% | xx xx.x% | xx xx.x%    | xx xx.x%    | xx xx.x% | xx xx.x% |
|             | Missing | xxx xx.x% | xxx xx.x% | xx xx.x% | xx xx.x%    | xx xx.x%    | xx xx.x% | xx xx.x% |
|             | Total   | xxx xx.x% | xxx xx.x% | xx xx.x% | xx xx.x%    | xx xx.x%    | xx xx.x% | xx xx.x% |

FOLDER\PROGRAM\OUTPUT: XXXXXX\XXXXXX.SAS\XXXXXX.LST

[1] The percentages for the baseline column were calculated using the baseline total as the denominator.

[2] For each row, the percentages were calculated using the number of subjects with a given grade at baseline as the denominator.

Worst post-baseline laboratory value was the worst grade observed post-baseline for a given subject.

DATE (TIME): MMDDYYYY (hh:mm)

## Incyte Corporation INCAGN 1876-101 Statistical Analysis Plan

PROTOCOL: INCAGN 1876-101 (Page n of N)
DRUG/INDICATION: INCAGN01876/Advanced or Metastatic Solid Tumors DATABASE VERSION: XXXXXX2016

TLF VERSION: Draft

Table 3.3.2.2

Shift Summary of Hematology Laboratory Values in CTC Grade - To the Worst Abnormal Value (Population: Part 2 FAS Population)

Laboratory Test (unit): xxxxxxxx (xxxxx)

|             | Base    | line[1]   |           | Wo       | rst Post-Ba | seline Valu | e [2]    |          |
|-------------|---------|-----------|-----------|----------|-------------|-------------|----------|----------|
| Cancer Type | Grade   | n (%)     | Grade 0   | Grade 1  | Grade 2     | Grade 3     | Grade 4  | Missing  |
| NSCLC       | Grade 0 | xxx xx.x% | XXX XX.X% | XX XX.X% | XX XX.X%    | XX XX.X%    | XX XX.X% | XX XX.X% |
|             | Grade 1 | XXX XX.X% | XXX XX.X% | xx xx.x% | xx xx.x%    | xx xx.x%    | xx xx.x% | xx xx.x% |
|             | Grade 2 | XXX XX.X% | XXX XX.X% | xx xx.x% | xx xx.x%    | xx xx.x%    | xx xx.x% | xx xx.x% |
|             | Grade 3 | XXX XX.X% | XXX XX.X% | xx xx.x% | xx xx.x%    | xx xx.x%    | xx xx.x% | xx xx.x% |
|             | Grade 4 | XXX XX.X% | XXX XX.X% | xx xx.x% | xx xx.x%    | xx xx.x%    | xx xx.x% | xx xx.x% |
|             | Missing | XXX XX.X% | XXX XX.X% | XX XX.X% | XX XX.X%    | XX XX.X%    | XX XX.X% | XX XX.X% |
|             | Total   | xxx xx.x% | XXX XX.X% | XX XX.X% | XX XX.X%    | XX XX.X%    | XX XX.X% | XX XX.X% |
| RCC         | Grade 0 | xxx xx.x% | xxx xx.x% | xx xx.x% | xx xx.x%    | xx xx.x%    | xx xx.x% | xx xx.x% |
|             | Grade 1 | XXX XX.X% | XXX XX.X% | xx xx.x% | xx xx.x%    | xx xx.x%    | xx xx.x% | xx xx.x% |
|             | Grade 2 | XXX XX.X% | XXX XX.X% | XX XX.X% | XX XX.X%    | XX XX.X%    | XX XX.X% | xx xx.x% |
|             | Grade 3 | XXX XX.X% | XXX XX.X% | xx xx.x% | xx xx.x%    | xx xx.x%    | xx xx.x% | xx xx.x% |
|             | Grade 4 | XXX XX.X% | XXX XX.X% | xx xx.x% | xx xx.x%    | xx xx.x%    | xx xx.x% | xx xx.x% |
|             | Missing | XXX XX.X% | XXX XX.X% | xx xx.x% | xx xx.x%    | xx xx.x%    | xx xx.x% | xx xx.x% |
|             | Total   | XXX XX.X% | XXX XX.X% | xx xx.x% | xx xx.x%    | xx xx.x%    | xx xx.x% | xx xx.x% |

FOLDER\PROGRAM\OUTPUT: XXXXXX\XXXXXX.SAS\XXXXXX.LST

[1] The percentages for the baseline column were calculated using the baseline total as the denominator.

[2] For each row, the percentages were calculated using the number of subjects with a given grade at baseline as the denominator.

Worst post-baseline laboratory value was the worst grade observed post-baseline for a given subject.

PROTOCOL: INCAGN 1876-101 (Page n of N)
DRUG/INDICATION: INCAGN01876/Advanced or Metastatic Solid Tumors DATABASE VERSION: XXXXX2016

TLF VERSION: Draft

Table 3.3.2.2

Shift Summary of Hematology Laboratory Values in CTC Grade - To the Worst Abnormal Value (Population: Part 2 FAS Population)

Laboratory Test (unit): xxxxxxxx (xxxxx)

|             | Base    | line[1]   | Worst Post-Baseline Value [2] |          |          |          |          |          |  |  |  |  |
|-------------|---------|-----------|-------------------------------|----------|----------|----------|----------|----------|--|--|--|--|
| Cancer Type | Grade   | n (%)     | Grade 0                       | Grade 1  | Grade 2  | Grade 3  | Grade 4  | Missing  |  |  |  |  |
| 
Total   | Grade 0 | xxx xx.x% | XXX XX.X%                     | XX XX.X% | XX XX.X% | XX XX.X% | XX XX.X% | XX XX.X% |  |  |  |  |
|             | Grade 1 | XXX XX.X% | XXX XX.X%                     | XX XX.X% | XX XX.X% | XX XX.X% | XX XX.X% | xx xx.x% |  |  |  |  |
|             | Grade 2 | XXX XX.X% | XXX XX.X%                     | xx xx.x% | XX XX.X% | XX XX.X% | XX XX.X% | xx xx.x% |  |  |  |  |
|             | Grade 3 | XXX XX.X% | xxx xx.x%                     | xx xx.x% | XX XX.X% | xx xx.x% | xx xx.x% | xx xx.x% |  |  |  |  |
|             | Grade 4 | XXX XX.X% | xxx xx.x%                     | xx xx.x% | xx xx.x% | xx xx.x% | xx xx.x% | xx xx.x% |  |  |  |  |
|             | Missing | xxx xx.x% | xxx xx.x%                     | xx xx.x% | xx xx.x% | xx xx.x% | xx xx.x% | xx xx.x% |  |  |  |  |
|             | Total   | xxx xx.x% | xxx xx.x%                     | xx xx.x% | xx xx.x% | xx xx.x% | xx xx.x% | xx xx.x% |  |  |  |  |

FOLDER\PROGRAM\OUTPUT: XXXXXXXXXXXX.SAS\XXXXXX.LST

DATE(TIME): MMDDYYYY(hh:mm)

- [1] The percentages for the baseline column were calculated using the baseline total as the denominator.
- [2] For each row, the percentages were calculated using the number of subjects with a given grade at baseline as the denominator.

Worst post-baseline laboratory value was the worst grade observed post-baseline for a given subject.

DATABASE VERSION: XXXXX2016

PROTOCOL: INCAGN 1876-101

DRUG/INDICATION: INCAGN01876/Advanced or Metastatic Solid Tumors

TLF VERSION: Draft

Table 3.3.3

Summary of Laboratory Values - Chemistry (Population: Part 2 FAS Population)

Laboratory Test (unit): xxxxxxxx (xxxxx)

\_\_\_\_\_\_

This table follows same shell as that for 3.3.1

FOLDER\PROGRAM\OUTPUT: XXXXXX\XXXXXX.SAS\XXXXXX.LST DATE(TIME): MMDDYYYY(hh:mm)

PROTOCOL: INCAGN 1876-101

(Page n of N)
DATABASE VERSION: XXXXX2016

DRUG/INDICATION: INCAGN01876/Advanced or Metastatic Solid Tumors

TLF VERSION: Draft

Table 3.3.4.1

Shift Summary of Chemisty Laboratory Values in CTC Grade - To the Worst Abnormal Value (Population: Part 1 FAS Population)

Laboratory Test (unit): xxxxxxxx (xxxxx)

This table follows same shell as that for 3.3.2.1

FOLDER\PROGRAM\OUTPUT: XXXXXX\XXXXXX.SAS\XXXXXX.LST DATE(TIME): MMDDYYYY(hh:mm)

[1] The percentages for the baseline column were calculated using the baseline total as the denominator.

[2] For each row, the percentages were calculated using the number of subjects with a given grade at baseline as the denominator.

Worst post-baseline laboratory value was the worst grade observed post-baseline for a given subject.

Page 157 of 187 06 JAN 2017

(Page n of N)

DATABASE VERSION: XXXXX2016

PROTOCOL: INCAGN 1876-101

DRUG/INDICATION: INCAGN01876/Advanced or Metastatic Solid Tumors

TLF VERSION: Draft

Table 3.3.4.2

Shift Summary of Chemisty Laboratory Values in CTC Grade - To the Worst Abnormal Value

(Population: Part 2 FAS Population)

Laboratory Test (unit): xxxxxxxx (xxxxx)

\_\_\_\_\_\_

This table follows same shell as that for 3.3.2.2

FOLDER\PROGRAM\OUTPUT: XXXXXX\XXXXXX.SAS\XXXXXX.LST DATE(TIME): MMDDYYYY(hh:mm)

[1] The percentages for the baseline column were calculated using the baseline total as the denominator.

[2] For each row, the percentages were calculated using the number of subjects with a given grade at baseline as the denominator.

Worst post-baseline laboratory value was the worst grade observed post-baseline for a given subject.

DATABASE VERSION: XXXXX2016

DATE (TIME): MMDDYYYY (hh:mm)

## Incyte Corporation INCAGN 1876-101 Statistical Analysis Plan

PROTOCOL: INCAGN 1876-101

DRUG/INDICATION: INCAGN01876/Advanced or Metastatic Solid Tumors

TLF VERSION: Draft

Table 3.4.1.1

Summary of Systolic Blood Pressure (mmHg) (Population: Part 1 FAS Population)

Dose Level(mg/kg) :0.01

|             |                                |            | Desc  | cripti | ve Sum | mary                    |                |     | Low  | Normal |                      | High |                      | Alert |                      |
|-------------|--------------------------------|------------|-------|--------|--------|-------------------------|----------------|-----|------|--------|----------------------|------|----------------------|-------|----------------------|
| Study Visit | Variable                       | N          | Mean  | STD    | Min    | Median                  | Max            |     | %    | N      | %                    | N    | %                    | N     | 90                   |
| Baseline    | Baseline                       | XXX        | XXX.X | xxx.x  | xxx.x  | XXX.X                   | XXX.X          | XXX | XX.X | XXX    | XX.X                 | XXX  | XX.X                 | XXX   | XX.X                 |
| Week xx     | Measured
Change
% Change | XXX
XXX | xxx.x | xxx.x  | xxx.x  | XXX.X
XXX.X
XXX.X | XXX.X
XXX.X | XXX | XX.X | XXX    | xx.x
xx.x
xx.x | XXX  | xx.x
xx.x         | XXX   | XX.X
XX.X
XX.X |
| Week xx     | Measured
Change
% Change | XXX
XXX | xxx.x | xxx.x  | xxx.x  | xxx.x
xxx.x
xxx.x | xxx.x
xxx.x | XXX | xx.x | XXX    | xx.x
xx.x
xx.x | XXX  | xx.x
xx.x
xx.x | XXX   | xx.x
xx.x
xx.x |

FOLDER\PROGRAM\OUTPUT: XXXXXX\XXXXXX.SAS\XXXXXX.LST

Note 1: Baseline is the last value collected before the first dose of study drug.

Note 2: The normal range for SBP is 85 - 160 mm/Hg. Alert values are defined as the measured value being outside the normal range and the percent change from baseline being > 25%.

Abbrevations: Min = minimum; Max = Maximum; STD = standard deviation;

DATABASE VERSION: XXXXX2016

DATE (TIME): MMDDYYYY (hh:mm)

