# 8.4. Vital Signs

Values at each scheduled visit, change, and percentage change from baseline for vital signs, including systolic blood pressure, diastolic blood pressure, pulse, respiratory rate, body temperature, and weight will be summarized descriptively. Change and percentage change from baseline will be calculated using the last nonmissing value before first dose of study drug (Day 1) as the baseline value.

Criteria for clinically notable vital sign abnormalities are defined in Table 6. The abnormal values for subjects exhibiting clinically notable vital sign abnormalities will be listed along with their assigned treatment group. Alert vital signs are defined as an absolute value outside the defined range and percentage change > 25%. The abnormal values for subjects exhibiting alert vital sign abnormalities will be listed.

**Table 6:** Criteria for Clinically Notable Vital Sign Abnormalities

| Parameter                | High Threshold | Low Threshold |
|--------------------------|----------------|---------------|
| Systolic blood pressure  | > 155 mmHg     | < 85 mmHg     |
| Diastolic blood pressure | > 100 mmHg     | < 40 mmHg     |
| Pulse                    | > 100 bpm      | < 45 bpm      |
| Temperature              | > 38°C         | < 35.5°C      |
| Respiratory rate         | > 24/min       | < 8/min       |

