### APPENDIX A. PLANNED TABLES AND FIGURES

This appendix provides a list of the planned tables and figures for the CSR. Standard tables will follow the conventions in the Standard Safety Tables initial version. Shells are provided for nonstandard tables. In-text tables are identical in structure and content as appendix tables, but follow a Rich Text Format.

The list of tables, figures, and the shells are to be used as guideline. Modifications of the list or shells that do not otherwise affect the nature of the analysis will not warrant an amendment to the SAP.

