|             |                                |            | Des   | cripti | ve Sum | mary                    |                |     | Low  | No  | rmal                 | Н   | igh                  | A   | lert                 |
|-------------|--------------------------------|------------|-------|--------|--------|-------------------------|----------------|-----|------|-----|----------------------|-----|----------------------|-----|----------------------|
| Study Visit | Variable                       | N          | Mean  | STD    | Min    | Median                  | Max            | N   | %    | N   | %                    | N   | %                    | N   | %                    |
| Baseline    | Baseline                       | XXX        | XXX.X | XXX.X  | XXX.X  | XXX.X                   | XXX.X          | XXX | XX.X | XXX | XX.X                 | XXX | XX.X                 | XXX | XX.X                 |
| Week xx     | Measured
Change
% Change | XXX
XXX | xxx.x | xxx.x  | xxx.x  | XXX.X
XXX.X
XXX.X | xxx.x
xxx.x | XXX | xx.x | XXX | xx.x
xx.x
xx.x | XXX | xx.x
xx.x
xx.x | XXX | xx.x
xx.x
xx.x |
| Week xx     | Measured
Change
% Change | XXX
XXX | xxx.x | xxx.x  | xxx.x  | XXX.X
XXX.X          | xxx.x
xxx.x | XXX | xx.x | XXX | xx.x
xx.x
xx.x | XXX | xx.x
xx.x
xx.x | XXX | xx.x
xx.x         |

FOLDER\PROGRAM\OUTPUT: XXXXXX\XXXXXX.SAS\XXXXXX.LST

DATE (TIME): MMDDYYYY (hh:mm)

Note 1: Baseline is the average of all measurements collected before the first dose of study drug.

Note 2: The normal range for RR is 600 - 1330 mm/Hg.

Alert values are defined as the measured value being outside the normal range and the percent change from Baseline being > 25%.

Abbreviations: Min = minimum; Max = Maximum; STD = standard deviation.

PROTOCOL: INCAGN 1876-101 (Page n of N)
DRUG/INDICATION: INCAGN01876/Advanced or Metastatic Solid Tumors DATABASE VERSION: XXXXX2016

TLF VERSION: Draft

Table 3.5.2.2

Summary of RR Interval (msec) from Central Lab 12-Lead ECG (Population: Part 2 FAS Population)

Cancer Type : Endometrium

|             |                                |            | Des   | cripti | ve Sum | mary                    |                         |     | Low  | No  | rmal                 | H:  | igh                  | A.  | lert                 |

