Summary of HR Interval (msec) from Central Lab 12-Lead ECG (Population: Part 2 FAS Population)

Cancer Type : Endometrium

|             |                                |            | Descriptive Summary |       |       |                         |                | Low |      | Normal |              | High |              | Alert |              |
|-------------|--------------------------------|------------|---------------------|-------|-------|-------------------------|----------------|-----|------|--------|--------------|------|--------------|-------|--------------|
| Study Visit | Variable                       | N          | Mean                | STD   | Min   | Median                  | Max            |     | %    | N      | %            | N    | 90           | N     | 90           |
| Baseline    | Baseline                       | XXX        | XXX.X               | XXX.X | xxx.x | XXX.X                   | XXX.X          | XXX | XX.X | XXX    | XX.X         | XXX  | XX.X         | XXX   | XX.X         |
| Week xx     | Measured
Change             | xxx
xxx |                     |       |       | xxx.x                   | xxx.x
xxx.x |     |      |        | xx.x
xx.x |      | xx.x
xx.x |       | xx.x
xx.x |
|             | % Change                       | XXX        | XXX.X               | xxx.x | xxx.x | XXX.X                   | XXX.X          | XXX | XX.X | XXX    | XX.X         | XXX  | XX.X         | XXX   | XX.X         |
| Week xx     | Measured
Change
% Change | xxx
xxx | xxx.x               | xxx.x | xxx.x | xxx.x
xxx.x
xxx.x | XXX.X
XXX.X | XXX | XX.X | XXX    | XX.X
XX.X | XXX  | XX.X
XX.X | XXX   | XX.X
XX.X |

FOLDER\PROGRAM\OUTPUT: XXXXXX\XXXXXX.SAS\XXXXXX.LST

Note 1: Baseline is the average of all measurements collected before the first dose of study drug.

Note 2: The normal range for HR is 40 - 100 mm/Hg.

Alert values are defined as the measured value being outside the normal range and the percent change from Baseline being > 25%.

Abbreviations: Min = minimum; Max = maximum; STD = standard deviation.

PROTOCOL: INCAGN 1876-101 DRUG/INDICATION: INCAGN01876/Advanced or Metastatic Solid Tumors DATABASE VERSION: XXXXX2016

TLF VERSION: Draft

Table 3.5.8.1

Summary of Outliers of QT, RR and QTcF Interval Values from Central Lab 12-Lead ECG by Visit (Population: Part 1 FAS Population)

Dose Level (mg/kg) : 0.01

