|            |                              |                             | Number (%) of Subjects |           |           |  |  |  |
|------------|------------------------------|-----------------------------|------------------------|-----------|-----------|--|--|--|
| Dose Level |                              |                             | QT                     | RR        | QTcF      |  |  |  |
| (mg/kg)    | Study Visit                  | Variable                    | (ms)                   | (ms)      | (ms)      |  |  |  |
| 0.01       | Baseline                     | Number of Subjects          | XXX                    | XXX       | XXX       |  |  |  |
|            |                              | Measured Value>=450 ms      | xx(xxx.x)              | xx(xxx.x) | xx(xxx.x) |  |  |  |
|            |                              | Measured Value>=480 ms      | xx(xxx.x)              | xx(xxx.x) | xx(xxx.x) |  |  |  |
|            |                              | Measured Value>=500 ms      | xx(xxx.x)              | xx(xxx.x) | xx(xxx.x) |  |  |  |
|            | Week xx                      | Number of Subjects          | XXX                    | XXX       | XXX       |  |  |  |
|            |                              | Measured Value>=450 ms      | xx(xxx.x)              | xx(xxx.x) | xx(xxx.x) |  |  |  |
|            |                              | Measured Value>=480 ms      | xx(xxx.x)              | xx(xxx.x) | xx(xxx.x) |  |  |  |
|            |                              | Measured Value>=500 ms      | xx(xxx.x)              | xx(xxx.x) | xx(xxx.x) |  |  |  |
|            |                              | Change From Baseline>=30 ms | xx(xxx.x)              | xx(xxx.x) | xx(xxx.x) |  |  |  |
|            |                              | Change From Baseline>=60 ms | xx(xxx.x)              | xx(xxx.x) | xx(xxx.x) |  |  |  |
|            | At any time during the study | Number of Subjects          | XXX                    | XXX       | XXX       |  |  |  |
|            |                              | Measured Value>=450 ms      | xx(xxx.x)              | xx(xxx.x) | xx(xxx.x) |  |  |  |
|            |                              | Measured Value>=480 ms      | xx(xxx.x)              | xx(xxx.x) | xx(xxx.x) |  |  |  |
|            |                              | Measured Value>=500 ms      | xx(xxx.x)              | xx(xxx.x) | xx(xxx.x) |  |  |  |

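### Two SAP output shells do not match the SAP's own limits: systolic blood pressure is capped at 160 instead of 155 mmHg, and RR intervals are counted against QT-type cut-offs

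*SAP*

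**What the plan says.** **Systolic blood pressure.** Protocol Table 16 and SAP Table 6 (section 8.4) both set the notable limits at above 155 and below 85 mmHg. SAP 8.4 builds the alert rule on those limits: "Alert vital signs are defined as an absolute value outside the defined range and percentage change > 25" percent. The shells for the SBP summaries, Table 3.4.1.1 (Part 1) and Table 3.4.1.2 (Part 2), have Low, Normal, High and Alert columns. Their second footnote reads "The normal range for SBP is 85 - 160 mm/Hg", and it defines an alert as a value outside that range with a change from baseline above 25%.

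**RR interval.** SAP Table 7 (section 8.5) treats RR as notable below 600 or above 1330 msec. The RR summary shells, 3.5.2.1 and 3.5.2.2, agree: "The normal range for RR is 600 - 1330 mm/Hg" (the unit is a misprint for msec). Shells 3.5.8.1 and 3.5.8.2 are titled "Summary of Outliers of QT, RR and QTcF Interval Values from Central Lab 12-Lead ECG by Visit". Their rows are "Measured Value>=450 ms", "Measured Value>=480 ms" and "Measured Value>=500 ms", plus changes from baseline of at least 30 and at least 60 ms. QT, RR and QTcF each have a column with count cells for every row.

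**Status of the shells.** SAP Appendix A says: "The list of tables, figures, and the shells are to be used as guideline". It adds that edits which leave the nature of the analysis unchanged do not call for a SAP amendment. The shells are marked as draft.

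**The concern.** The SAP gives two upper limits for SBP, and therefore two Alert rules for one variable. A programmer who follows section 8.4 for the listings and the shell for the table would produce outputs that disagree, with the table always showing the smaller count.

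The RR problem is different. The three cut-offs fall below the whole of the SAP's normal RR range, so an outlier column for RR would count normal readings and leave out the shortest intervals. A reader of the study report could take a high count in that column for a cardiac signal, or stop trusting the table.

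What is at stake is the accuracy and consistency of some supporting safety tables.

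**Working it through.** No derived figure in the plan has to be reproduced here. The check compares the limits and lists which values they classify differently.

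**Step 1: SBP classification.** Inputs: high if above 155 mmHg (SAP Table 6, Protocol Table 16); high if above 160 mmHg (shell footnote, range read as inclusive). The low limit is 85 mmHg in both. In whole mmHg the rules disagree for 156, 157, 158, 159 and 160. All five are notable under Table 6 and Normal under the shell, so the discrepancy runs in one direction.

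**Step 2: SBP alerts.** Percentage change = (value − baseline) / baseline × 100.

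| Baseline | Value | Change | Alert under SAP 8.4 | Alert under shell |
|---|---|---|---|---|
| 120 | 158 | 38/120 = 31.7% | Yes | No |
| 124 | 156 | 32/124 = 25.8% | Yes | No |
| 128 | 160 | 32/128 = 25.0% | No (not above 25%) | No |

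An alert is lost only when the reading is above 155 and up to 160 and the baseline is below 160/1.25 = 128 mmHg.

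**Step 3: possible size for SBP.** The documents give no SBP distribution. As an assumption only, take SBP as normal with mean 130 mmHg:

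| Assumed SD | Share above 155 | Share above 160 | Difference |
|---|---|---|---|
| 12 | 1.9% | 0.6% | 1.2 points (from unrounded shares) |
| 15 | 4.8% | 2.3% | 2.5 points |
| 18 | 8.2% | 4.8% | 3.5 points (from unrounded shares) |

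**Step 4: is 160 a deliberate second convention?** The other vital-sign footnotes match Table 6: diastolic pressure 40 to 100, pulse 45 to 100, respiratory rate 8 to 24, temperature 35.5 to 38. Only SBP departs. An amendment does not explain it either, because Table 6 and the shells are in the same SAP.

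**Step 5: RR.** Heart rate in bpm = 60000 / RR in ms.

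- Cut-offs: 60000/450 = 133, 60000/480 = 125, 60000/500 = 120 bpm. Each row counts any heart rate at or below that figure.
- Table 7 limits: 60000/600 = 100 and 60000/1330 = 45 bpm.
- Since 600 is above 500, every RR from 600 to 1330 ms meets all three rows. So does every RR above 1330 ms, and every low RR from 500 to just under 600 ms.
- An RR below 450 ms, which Table 7 calls low, meets none.

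The rows therefore cannot separate low, normal and high RR as Table 7 defines them. The change rows do no better: from 800 ms (75 bpm), a rise of 30 ms gives 60000/830 = 72.3 bpm, a shift of under 3 bpm.

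**The case against.** The strongest reply is that nothing has been miscounted. The shells are drafts and a guideline, and the governing text is right where it defines abnormality. Section 8.4 bases its listings on Table 6, section 8.5 bases its listing of notable ECGs on Table 7, and shells 3.5.2.1 and 3.5.2.2 already classify RR by 600 to 1330. Shell 3.5.8 states no normal range for RR, so its RR column is better described as uninformative than as a rival definition. All of this stands, and it keeps the point minor. It does not remove the point, because the footnotes and the RR cells would go into the outputs if programmed as written, and nothing in the SAP says which SBP limit prevails.

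Four stronger readings are tempting and not supported.

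- A reader might infer that reported counts are wrong. No counts exist in these documents.
- A reader might infer that close to all subjects would be RR outliers at baseline. That needs a heart-rate distribution, which the documents do not give. They support only the statement about values between 600 and 1330 ms.
- A reader might infer that the primary endpoint is compromised because it concerns safety. Protocol 2.2.1 and SAP 2.3.1 define it by the frequency, duration and severity of adverse events, which these tables do not supply.
- A reader might extend the criticism to the QT and QTcF columns of shell 3.5.8. Those are a separate categorical display and do not conflict with Table 7.

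**Conclusion.** The inconsistency is real and minor. If programmed from the shells, the High and Alert columns of Tables 3.4.1.1 and 3.4.1.2 would under-count relative to SAP 8.4 for readings above 155 and up to 160 mmHg. The RR column of Tables 3.5.8.1 and 3.5.8.2 would count every RR in the SAP's normal range in all three cut-off rows and miss RR below 450 ms.

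The number of readings affected cannot be found from the documents. Under the assumed normal distributions, the SBP gap is roughly 1 to 3.5 percentage points of readings, which is an illustration and not an estimate for this trial. The conclusion on classification needs no such assumption. It rests only on the printed limits and on reading the footnote range as inclusive.

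DLT assessment, dose escalation, adverse event reporting and the Simon two-stage decisions do not use these tables and are unaffected. The table list in Appendix A does not mark the SBP and ECG tables for in-text use.

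**What to change.** - In shells 3.4.1.1 and 3.4.1.2, change the SBP range to 85 to 155 mmHg, so that the summary, the Alert column and the listings follow SAP Table 6 and Protocol Table 16.
- In shells 3.5.8.1 and 3.5.8.2, remove RR from the title and columns, or give it its own rows at the Table 7 limits (below 600, above 1330 msec). Leave QT and QTcF as they are. Make the matching change to the titles in the Appendix A table list.
- In the same pass, correct the unit in the ECG footnotes from mm/Hg to msec.

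The cost is a few shell edits before programming. By Appendix A's own terms they should need no SAP amendment, since the nature of the analysis does not change.
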